To date, several studies have reported that rTMS reduced cue craving in nicotine dependence ¹⁹⁻²². However, these studies are limited by small sample sizes, variation in stimulation parameters, and in some cases the lack of sham-controlled design and objective measures of tobacco smoking. Furthermore, in all of these studies, stimulation location was targeted to a fixed brain region based on standard skull landmarks. rTMS studies in depression have showed that antidepressant effects are likely depend on coil positioning ^{23, 24}. Personalized coil placement based on a pre-treatment MRI has the potential to enhance outcomes. Additionally the duration or reduced craving following rTMS has yet to be examined. Taken together, while rTMS has demonstrated promise in facilitating smoking cessation, further double-blind investigation is required to determine optimal stimulation parameters and the duration of effect of rTMS in smokers. Furthermore, MRI guided TMS may help us to identify the optimal stimulation location to enhance the effectiveness of the treatment.

This R21 will build on exciting pilot work and advance our knowledge concerning the potential utility of rTMS in smoking cessation by conducting a controlled, double-blind method comparing the impact of ten daily treatments of active rTMS and sham rTMS, on cue-induced craving and cigarette consumption in nicotine-dependent cigarette smokers with extensive monitoring of side effects and smoking outcomes. We propose to directly stimulate the left DLPFC with Brainsight in smokers. In the two years of project, we plan to recruit 42 cigarette males and females of all ethnic and racial groups between the ages of 18 and 60 to participate in the study. Specific Primary Aims include:

Aim 1: To determine under rigorous experimental conditions, whether 10 MRI guided rTMS of left DLPFC treatment sessions over a 2 week period result in superior clinical outcomes compared to sham rTMS in smoking cessation.

Hypothesis 1: We hypothesize that 10 rTMS sessions (15 minutes 10 Hertz active rTMS at 100% resting motor threshold-rMT) over DLPFC will significantly reduce cue-elicited craving and cigarettes per day as compared to sham rTMS.

Aim 2: To evaluate the longevity of clinical benefit of 10 rTMS sessions on smoking measures including cigarettes per day and level of nicotine dependence with following-up 3 months after the last rTMS session.

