In conclusion, nicotine dependence is the leading preventable cause of mortality in the world today. In spite of treatment advances, there is much room for improvement in the therapeutic approaches. Recent advances make it possible to utilize rTMS to modify behavior, cognitions and regional brain activity. Preliminary trials suggest potential therapeutic applications of rTMS in the area of nicotine dependence. The purpose of this proposal is to preliminarily explore the efficacy of 10 daily MRI-guided DLPFC rTMS in decreasing cue-induced craving and cigarette consumption in nicotine-dependent cigarette smokers. Information gathered through this study will inform future studies in terms of optimal parameters for the use of rTMS in the treatment of nicotine-dependent smokers.

2. Innovation

As mentioned above, several previous studies have demonstrated that rTMS applied to the lateral or medial prefrontal cortex can impact cue craving and/or consumption of cigarettes ¹⁹⁻²². However, in all studies to date the form of sham TMS did not cause similar scalp or facial sensation compared to real TMS leading to questions about the validity of the comparisons. In the proposed study, we will use an active E-sham condition ^{41, 42} which produces scalp/facial sensations that are comparable to rTMS. In addition, studies to date have used a 5 cm rule for prefrontal location determination which is imprecise and as many as 30% of participants may have been treated over the supplementary motor area rather than the prefrontal cortex ⁴³. Finally, a meta-analysis ⁴⁴ and a prospective clinical trial ⁴⁵ suggest that use of a greater number of rTMS stimulations may be more effective in depression treatment. Previous rTMS studies in smoking used 1000 pulses, much less than the dosage of TMS pulses demonstrated to be efficacious in depression, and higher doses have not been explored. This R21 proposal is innovative in three respects: this is the first time that a double blind rTMS study will be compared to an active E-sham stimulation in smokers; in addition, we will use MRI to determine stimulation site over prefrontal cortex; finally, we will employ more stimulation pulses (3000 pulses) than previous studies, allowing us to quantitatively and qualitatively investigate both short and longer term effects of rTMS in smoking cessation.

RESEARCH PLAN

[figure not shown]

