Treatment sessions last for 15 minutes (60 trains) with 3000 pulses. The masked randomization status will be maintained for the entire enrollment period, until the last subjects have completed the study in the second year. Cue craving rating and cigarette consumption will be assessed before and after active rTMS or sham rTMS for 10 days. All participants will have two follow-up visits at 1 week and 1 month after the last rTMS session and a follow-up phone after 3 months of the last rTMS session. Safety will be assessed by collecting information on all relevant adverse events experienced.

2. Study Subjects and Entry Criteria Inclusion Criteria: Subjects will:

- (1). Be between the ages of 18 and 60 years old.
- (2) Smoke 10 or more cigarettes per day and have a carbon monoxide (CO) level > 10 ppm indicative of recent smoking.

- (3) Not received substance abuse treatment within the previous 30 days.
- (4) Meet criteria for nicotine dependence as determined by the FTND.
- (5) Be in stable mental and physical health.
- (6) If female, test non-pregnant and use adequate birth control.
- (7) No evidence of focal or diffuse brain lesion on MRI.
- (8) Be willing to provide informed consent.
- (9) Be able to comply with protocol requirements and likely to complete all study procedures.

Exclusion Criteria:

Subjects with:

- (1) Current dependence, defined by DSM-V criteria, on any psychoactive substances other than nicotine or caffeine.
- (2) Contraindication to MRI (e.g., presence of metal in the skull, orbits or intracranial cavity, claustrophobia).
- (3) Contraindication to rTMS (history of neurological disorder or seizure, increased intracranial pressure, brain surgery, or head trauma with loss of consciousness for > 15 minutes, implanted electronic device, metal in the head, or pregnancy).
- (4) History of autoimmune, endocrine, viral, or vascular disorder affecting the brain.
- (5) History or MRI evidence of neurological disorder that would lead to local or diffuse brain lesions or significant physical impairment.
- (6) Unstable cardiac disease, uncontrolled hypertension, severe renal or liver insufficiency, or sleep apnea.
- (7) Life time history of major Axis I disorders such as: Bipolar Affective disorder (BPAD), Schizophrenia, Post-traumatic Stress disorder (PTSD) or Dementia or Major Depression.
- (8) Self report of >21 standard alcohol drinks per week in any week in the 30 days prior to screening.

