convenience by using the "pause" selection on the device. However, in the event that an incomplete treatment is given, this information will be recorded. In the event that a treatment is missed, the following procedure will be followed: 1 day missed, or 2 days missed in a row—continue into the subsequent week to complete the missed days. Evaluation will still occur after every 5 treatments. 3 or more days in a row—treatment must be aborted and the subject discontinued from their current phase and likely dropped from the study. (2)Monitoring for seizure activity: During the treatment procedure, the treatment administrator must observe the subject closely for any sign of imminent seizure activity or muscle twitching. The administrator must be an individual trained to be perceive to warning signs, and will be familiar with the emergency management of seizure activity. Emergency equipment (oxygen, suction, CPR equipment) will be readily available in the treatment suite. (3)Recording of adverse events: During the treatment procedure, the administrator will assess for and record any adverse events. Prior to leaving the facility following each treatment, the subject will be assessed for the occurrence of adverse events by a qualified individual who is masked to the subject's assigned treatment group. Immediately prior to, and following each TMS treatment session, all patients will complete a Visual Analog Scale to assess within session changes in side effects.

8. Assessments and Instruments (Specific Aim 1 & 3)

- 1). Craving Assessment: Upon arrival at the laboratory, participants will be observed smoking their last cigarette before beginning to complete questionnaires. Immediately prior to, and following each TMS treatment session, all patients will complete a Likert Visual Analog Cue Craving Scale to assess within session changes in subjective craving.
- 2). QSU Brief: Cue presentation and Craving Assessment: Scenic images, neutral control images and cigarette smoking cue images are presented in four blocks. Immediately after viewing each block of cue images, subjects will completed an adapted QSU-B utilizing a computerized visual analog scale (CVAS) designed to assess craving. Each question is followed by a CVAS (the range of 0 and 100).
- 3). Carbon Monoxide: Subjects will be measured CO before TMS daily and at 1 week and 1 month follow-up visits.

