- 4). Weekly Assessments: At the end of the 5th and the 10th treatment and 1 week and 1 month follow-up visits, subjects will complete FTND, MNWS-R, Tobacco diary, mCEQ and adverse events.
- 5). At the end of the experiment, subjects will be asked what treatment (active or sham) he/she believes was completed.
- **9. Follow-up (Specific Aim 2).** The treatment period of the study will conclude on the end of two weeks. Participants will then enter the follow-up phase of the study. The two follow-up visits will be scheduled one 1 week and 1 month after the 10th rTMS session. Data will include craving ratings, tobacco diary, CO, QSU-B and FTND. We will conduct a follow-up phone survey of participants 3 months after the 10th treatment. Cigarette consumption will be evaluated by asking: 'How many cigarettes do you now smoke on an average day?'. Craving will be assessed by asking: 'How much do you want to smoke a cigarette right now on a scale from 1 to 10?' and "When was your last cigarette?'. Nicotine dependence will be assessed by the FTND.
- 10. Data Analyses. All data will be analyzed in consultation with Data Coordination Unit (DCU) at MUSC. Quantitative measures of nicotine dependence: Craving rating panel, Tobacco diary, CO, QSU-B and FTND. Side effects: Following standard procedures, frequency and severity measures of side effects will be constructed from the clinical measures. Significance testing: All tests will be two-sided, performed at significance α =0.05, except where noted. The statistical approach will use an ANOVA for each outcome variable. Some data may be longitudinal as well as cross-sectional and we will include random effects to account for within-subject correlation.

Power Analysis. The primary efficacy of rTMS for this study will be the abstinence rate and the number of cigarettes smoked per day at the end of treatment. One previous study of rTMS reported that 10 sessions of rTMS significantly reduced the number of cigarettes per day by the 10^{th} treatment ($18.11 \pm 2.61 \text{ vs.} 10.71 \pm 2.19$) ¹⁹. A power analysis was conducted based upon this two group design, a power of 0.8, and an alpha level of 0.05; a significant difference is anticipated with 18 subjects in each group. The attrition rate in the above mentioned study was 8%. The attrition rate for our previous study was 12% ³¹. According to the attrition

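### The outcomes labelled primary are not the pair in Hypothesis 1, and no success rule says which result confirms Aim 1

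*Combined protocol and SAP*

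**What the plan says.** Aim 1 (Specific Aims) asks whether ten MRI-guided sessions "result in superior clinical outcomes compared to sham rTMS in smoking cessation". Hypothesis 1, directly below it, predicts that active treatment "will significantly reduce cue-elicited craving and cigarettes per day as compared to sham rTMS". The purpose statement that closes the Significance section uses the same pair: the study is to "preliminarily explore the efficacy of 10 daily MRI-guided DLPFC rTMS in decreasing cue-induced craving and cigarette consumption".

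The Power Analysis paragraph in section 10 (Data Analyses) reads differently: "The primary efficacy of rTMS for this study will be the abstinence rate and the number of cigarettes smoked per day", both at the end of treatment. Craving is absent there, and abstinence is absent from Hypothesis 1.

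Section 10 sets every test at two-sided 0.05, allows for noted exceptions (none is noted), and plans one ANOVA per outcome. It gives no testing order, alpha split or success rule.

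The outcomes themselves are only partly defined:

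- **Craving** is measured by two instruments in section 8: "Immediately prior to, and following each TMS treatment session, all patients will complete a Likert Visual Analog Cue Craving Scale", and "Immediately after viewing each block of cue images, subjects will completed an adapted QSU-B". Section 4 adds that the QSU-B yields a total and two factor scores. No score or time point is chosen.
- **Abstinence** has no time window and no CO or cotinine limit. The only CO threshold is an entry criterion: "carbon monoxide (CO) level > 10 ppm indicative of recent smoking".
- **Cigarettes per day** is recorded in a daily diary (section 4) and assessed after sessions 5 and 10 (section 7). No averaging window is given, and no choice between level and change from baseline.

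**The concern.** Three outcomes have some claim to decide Aim 1, and only cigarettes per day is in both pairs. With no success rule, the result that confirms the aim could be picked after the data are seen. Two consequences follow, depending on how the word joining each pair is read:

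- If one success is enough, the 5% error rate is not assured.
- If all must succeed, error is controlled, but the stated power is not the power of the study, because it was worked out for one outcome only.

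The loose definitions of all three outcomes add further room for choice. The stakes are moderate. This is a preliminary 42-person study and no approval depends on it. But Aim 1 is worded as a superiority determination, and the results are meant to inform a larger, more definitive trial.

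**Working it through.** **1. The plan's own figures.** Section 10 gives 18 per group at power 0.8 and alpha 0.05, and 12% attrition: 18 / (1 − 0.12) = 20.45, rounded up to 21, or 42 in total. That step reproduces.

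The 18 does not follow from the printed means alone. The difference is 18.11 − 10.71 = 7.40. If the ± values are SDs, the pooled SD is √((2.61² + 2.19²)/2) = 2.41, so d = 3.07 and about 3 per group would do. If they are standard errors, the answer depends on the cited study's arm size, which the documents do not give; an assumed 10 per arm gives 18. This is a separate matter. It is used here only to set a range for the SD: 18 per group detects d = 0.961 at 80% power, which for a difference of 7.40 means an SD of 7.40 / 0.961 = 7.70. The range used below is therefore 2.4 to 7.7. All power inputs concern cigarettes per day.

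**2. If any one outcome is enough (not stated in the plan).**

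*Three outcomes.* The ceiling is 3 × 0.05 = 15%, provided each test holds its 5%. Independent tests give 1 − 0.95³ = 14.3%. Simulated normal test statistics with equal correlation (1,000,000 draws) give:

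| Assumed correlation | Any-one error |
|---|---|
| 0.3 | 13.6% |
| 0.5 | 12.5% |
| 0.7 | 10.9% |

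This treats abstinence as a continuous outcome tested at a full 5%, so it probably overstates the error where abstinence is rare (see step 4).

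*Craving and cigarettes per day only.* The ceiling is 2 × 0.05 = 10%. Two-group t-tests at 18 per group give 9.6%, 9.1% and 8.4% at correlations 0.3, 0.5 and 0.7.

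*Abstinence and cigarettes per day only.* These are tied together, because abstainers smoke zero. Simulation at 18 per group assumed null abstinence of 5–30%, with the remaining smokers at a mean of 10.71–18.11 and an SD of 2.4–7.7 cigarettes per day. With the planned ANOVA, any-one error is 4.4–8.7%.

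None of these figures includes choosing among craving scores or time points, which would add to the error.

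**3. If both labelled primaries must succeed.** In the same simulation, both ANOVAs are significant under the null in 0.15–3.95% of runs, so error is controlled. Joint power cannot exceed the power for abstinence. The documents give no abstinence rates, so sham rates are assumed. Exact enumeration at 18 per group gives the active-arm abstinence needed for 80% power:

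| Assumed sham abstinence | Planned ANOVA | Fisher's exact test |
|---|---|---|
| 5% | 42% | 47.5% |
| 10% | 51% | 56.5% |
| 20% | 63% | 68.5% |

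For a smaller effect, such as 5% against 25%, power at 18 per group is about 39% by the normal approximation (25% by Fisher).

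**4. Exact size of ANOVA on 0/1 abstinence, 18 per group.** At null abstinence of 5%, 10%, 20% and 30% it is 0.9%, 3.3%, 4.75% and 4.99%. At 35–50% it is 5.5–6.5%.

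**The case against.** The best reply is that there is no contest between primaries. Only the Power Analysis paragraph uses that label; a hypothesis and a purpose statement do not rank endpoints. On that reading abstinence and cigarettes per day are the primaries, craving is a further hypothesised outcome, and Aim 1's reference to smoking cessation fits. Much of this stands: the documents do not name craving as a rival primary. It does not settle the point, because the labelled pair still has no success rule and abstinence still has no definition. Craving also remains part of the hypothesis that tests Aim 1.

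A second reply is that formal multiplicity control is optional in a preliminary study. That lowers the priority, but a study that tests at 0.05 and feeds a larger trial should still say which p-value is its result.

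Three stronger readings are tempting and are not supported:

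- **The error rate is 11–14%.** That requires an any-one rule, which the plan does not state. If all must succeed there is no inflation.
- **Abstinence at session 10 cannot be observed.** Section 8 says "participants will be observed smoking their last cigarette before beginning to complete questionnaires" but does not say at which visits. The difficulty arises only if session 10 is included.
- **ANOVA on a yes/no outcome invalidates the abstinence test.** Its size does not exceed 5% up to about 30% null abstinence, and the excess above that is small.

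**Conclusion.** The point holds and should be fixed; its consequence is moderate. The pair labelled primary differs from the pair in Hypothesis 1 and the purpose statement, and no rule says which results confirm Aim 1.

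The plan does not say which of the two consequences applies: a possible any-one error above 5% (about 11–14% across three outcomes, 4.4–8.7% within the labelled pair), or controlled error with a joint power that is unstated and, unless the abstinence effect is very large, well below 0.8. The mismatch and the missing rule are read directly from the text. The sizes depend on assumed correlations, abstinence rates, means and SDs, since the documents supply inputs for cigarettes per day only.

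**What to change.** Before unblinding:

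1. **Primary.** Name cigarettes per day at the end of treatment as the single primary outcome, tested at two-sided 0.05. It is the only outcome in both pairs and the only one with power inputs. Define it from the tobacco diary: for example, mean cigarettes per day over a stated window ending at session 10, compared between arms with baseline cigarettes per day as a covariate.
2. **Secondaries.** Report abstinence and craving with 95% confidence intervals, or test them in a stated order only if the primary is significant.
3. **Abstinence.** Define it as zero diary cigarettes over a stated window plus a stated CO or cotinine limit, and say how the cigarette observed on arrival is handled. If ANOVA is kept, note that its size passes 5% above about 30% null abstinence.
4. **Craving.** Choose one score at a visit where it is already scheduled, such as the Likert rating after session 10. If the adapted QSU-B is preferred, confirm its visit first: Table 1 marks it by week only, section 8 gives no day for the cue task, and the list of assessments after sessions 5 and 10 omits it.
5. **Consistency.** Align Hypothesis 1, the purpose statement and section 10.

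The cost is wording and three outcome definitions. Sample size, visits and data collected stay the same if the chosen scores are ones already scheduled. The downside is that a positive craving or abstinence result alone would no longer confirm Aim 1.

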Hypothesis 2: We will predict that the effects of rTMS will dissipate over 3 months following-up time in some smokers. We also will predict that the effects of rTMS will last more than 3 months in other smokers. The following-up data will provide the best fit of the relapse-time data relative to a variety of parametric alternatives.

Aim 3: To demonstrate whether the active rTMS and sham groups differ significantly in side effect profiles, and whether the frequency and severity of side effects decreases over the course of treatment.

Hypothesis 3: The frequency and severity of side effects will not differ between the active rTMS and sham groups, and decreases over the course of the treatment, suggesting adaptation or tolerance.

RESEARCH STRATEGY

1. Significance

Nicotine dependence remains a significant public health concern. In 2011, the World Health Organization (WHO) reported that tobacco use continues to be the leading global cause of preventable death, killing nearly 6 million people and causing hundreds of billions of dollars of economic damage worldwide each year ²⁵. In the United States, cigarette smoking is the leading preventable cause of mortality accounting for approximately 1 out of every 5 deaths ¹. On average, smokers die 13 to 14 years earlier than nonsmokers ²⁶. Cigarette smoking is the most common form of tobacco use and 45.3 million persons (19.3% of the population) are current cigarette smokers. Additionally the estimates for average annual smoking-attributable productivity losses are \$96.8 billion and the total economic burden of smoking is approximately \$193 billion per year ²⁷.

The 2010 National Health Interview Survey revealed that approximately 70% of current smokers want to quit and 41% have tried to quit, however few of these attempts were successful with only 4.7% of current smokers able to stop smoking for at least three months ². Despite the availability of therapeutic options for smoking cessation, only 6% of the 35 million smokers who report wanting to quit each year are successful in doing so for more than a month ^{8, 9}. **Clearly, there is room for improvement in smoking cessation.**

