One particularly salient feature of nicotine-dependent cigarette smoking is the ability of associated environmental cues to elicit craving and cigarette-seeking behaviors. The systematic study of craving has occurred primarily via cue reactivity paradigms ^{28, 29} in which nicotine-dependent individuals are exposed to cues previously associated with smoking (e.g., cigarette, lighter, ashtray) and subjective craving and physiological reactions are measured ^{30, 31}. Numerous laboratory-based studies, including studies conducted in our laboratories at Medical University of South Carolina (MUSC), have demonstrated that exposure to smoking-related cues elicits robust craving and measurable physiological reactivity among smokers ³². These findings represent some of the most compelling evidence in support of a causal relationship between craving and cigarette smoking. Thus, the concept of craving has become an important focus of studies on smoking behavior, relapse and smoking cessation treatment. In conclusion, these findings imply that escalation of withdrawal symptoms, craving, and smoking urges during a quit attempt may contribute to smoking relapse. The reduction of cue craving and smoking urges may facilitate the treatment of nicotine dependence and prevent relapse during a smoking quit attempt.

Transcranial magnetic stimulation (TMS) is a noninvasive (and relatively painless) brain stimulation technology that can focally stimulate the brain of an awake individual ^{33, 34}. A localized pulsed magnetic field transmitted through a TMS coil is able to focally stimulate the cortex by depolarizing superficial neurons ^{35, 36} inducing electrical currents in the brain ¹⁶. If TMS pulses are delivered repetitively and rhythmically, the process is called repetitive TMS (rTMS). rTMS for the treatment of depression was approved for one manufacturer by the U.S. Food and Drug Administration (FDA) in October, 2008 ^{37, 38} and for a different device in January 2013. Researchers are investigating rTMS potential treatment effects in other neuropsychiatric disorders (schizophrenia, pain, alcohol, cocaine, stroke) ³⁹. **Taken together, TMS techniques could be used to improve the efficacy of smoking cessation.**

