- 6. **MRI Scanning Procedures.** At baseline and at the TMS 10 visit, subjects will have a 3.0 T MRI scan of the head with vitamin E tablets placed over the Abductor Pollicis Brevis (APB) motor cortex. Vitamin E tablets are easily visible on the MRI without artifact. We will acquireT1, T2, and FLAIR images to rule out coincidental pathology. These will be followed by high-resolution 3D SPGR images through the whole head (124 contiguous sagittal 0.9 mm slices) for accurate localization.

7. TMS Procedures

- 1). All TMS procedures will be performed by a highly trained faculty or staff member of the Brain Stimulation Laboratory at MUSC under the supervision of a licensed M.D. with specialized training in TMS delivery. All participants will be fitted with a white lycra swim cap at the initial setting. This cap will be worn during the 1st TMS sessions and in the MRI scanner in order to insure proper placement of the TMS coil across visits. The motor cortex will be located and the TMS motor threshold will be assessed. With Brainsight™ neuronavigation software (Rogue Research, Montreal, Canada), the TMS coil will then be moved over the left prefrontal cortex. Using a black permanent marker, landmarks will be placed on the cap to allow for proper refitting for following TMS sessions.
- 2). Treatment parameters and grouping The time in the chair and the number of pulses on the head will be the same for all subjects. Active or sham TMS will be the only difference. The sham group only receives sham at all treatments. Stimulation frequency for all active subjects: 10 Hertz Pulse train duration (on time) 5 seconds, Inter-train interval (off time) 10 seconds (15 second cycle time), Power (intensity) level 100% rMT, Total 60 trains, 15 minutes, Total pulses 3000 per day, 3000 x 10 = 30000 pulses for 10 sessions.

Group 1 = Sham treatment over DLPFC Group 2 = Active treatment over DLPFC

- 3). Treatment Scheduling All participants will be treated Monday Friday for 10 treatments. Ideally, all participants will be treated in the morning, at the same time of day throughout the study, with a note of any time deviation in the case report form (CRF). Each treatment will last about 35 minutes, including 15 minutes of rTMS or sham treatment delivery and 20 minutes pre and post craving rating (10 minutes each). At the end of 5th and 10th rTMS sessions, subjects will be assessed for craving and cigarette consumption.

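### Abstinence is a primary outcome and relapse time is to be modelled, but the visible plan starts no quit attempt and gives no time zero, so neither can be interpreted as specified

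*Combined protocol and SAP*

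**What the plan says.** Several places describe a cessation trial.

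- Specific Aims, Aim 1, asks whether ten sessions "result in superior clinical outcomes compared to sham rTMS in smoking cessation".
- Section 10, Power Analysis: "The primary efficacy of rTMS for this study will be the abstinence rate". The same sentence adds daily cigarette consumption, with both judged when treatment finishes.
- Hypothesis 2: "The following-up data will provide the best fit of the relapse-time data relative to a variety of parametric alternatives".
- Section 1, Significance, gives the rationale that lower craving "may facilitate the treatment of nicotine dependence and prevent relapse during a smoking quit attempt".

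Other places describe a reduction trial.

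- Hypothesis 1 says that active rTMS "will significantly reduce cue-elicited craving and cigarettes per day as compared to sham rTMS". It does not name abstinence.
- Aim 2 concerns "smoking measures including cigarettes per day and level of nicotine dependence with following-up 3 months after the last rTMS session".
- In Human Subjects Research, section 5 (Potential Benefits), the expected gain for participants is fewer cigarettes and less craving. Quitting is not mentioned.
- Section 8, item 1 (Craving Assessment), has participants watched while they smoke a cigarette on arrival at the laboratory, before the questionnaires. It does not say at which visits.

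The population is treatment-seeking (Experiment Approach, section 1). Table 1 schedules the tobacco diary, CO and urine cotinine during treatment and at the 1-week and 1-month visits. The 3-month telephone contact asks when the last cigarette was smoked (section 9).

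**The concern.** Abstinence and relapse are events in a quit attempt. Abstinence is most informative when people have tried to stop, and relapse time exists only for people who have stopped, counted from a defined moment. The visible plan provides neither the attempt nor the moment. A site that follows it delivers ten sessions to people who may or may not decide to stop, at whatever time suits them.

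Two results are at stake. If few people in either arm are abstinent, the trial cannot tell whether rTMS failed to support quitting or whether few people tried. Any relapse curve would pool self-chosen stop dates, in a subset of participants formed after randomisation. If the observed cigarette is part of every session, the procedures also require smoking on the day on which abstinence is to be assessed.

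**Working it through.** **1. Is a quit attempt started anywhere?** I went through the sections that could hold one.

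- General Design, Baseline Evaluation, Table 1, TMS Procedures, Assessments and Instruments, and Follow-up: no quit day, no request to stop, no cessation counselling.
- Section 3, item 2: a cessation referral, but only for people who do not enter the study.
- Section 10: no time window and no CO or cotinine cut-off for abstinence; no relapse event and no starting point.

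**2. What does each outcome need?**

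| Outcome | Needs a quit date? | Consequence here |
|---|---|---|
| Cigarettes per day, craving, FTND | No | Unaffected |
| Abstinence at end of treatment | Not for a fair comparison, but needed to read a null result | Likely few events; ambiguous if low in both arms |
| Relapse time | Yes, plus a defined event | Undefined for anyone who never stops; no common origin |

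**3. What was the sample size set on?** Only cigarettes per day: 18.11 ± 2.61 versus 10.71 ± 2.19.

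- Difference 18.11 − 10.71 = 7.40. Root-mean-square spread √[(2.61² + 2.19²)/2] = 2.41.
- If ± is an SD, d = 7.40/2.41 = 3.07, and 80% power at two-sided 0.05 needs 2 per group (normal) or 3 (t). The stated 18 is not reproduced.
- If ± is a standard error with 10 per arm (my assumption), SD = 2.409 × √10 = 7.62, and the t calculation gives 18.
- Attrition: 18/(1 − 0.12) = 20.5, rounded up to 21 per group, 42 in total. This reproduces.

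The point does not depend on how ± is read. What matters is that abstinence has no power statement.

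**4. How few abstainers might there be?** The documents give no abstinence rate for either arm, so I assume a sham rate of 4.7%, 6% or 10%. Section 1 quotes the first two for smokers at large over longer periods. They are illustrations, not estimates for this trial.

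- Expected abstainers = n × p. Chance of none = (1 − p)^n.
- Power (normal) = Φ{[Δ − 1.96√(2p̄(1−p̄)/n)] / √[(p₁(1−p₁) + p₂(1−p₂))/n]}. Fisher power is exact enumeration.

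| Sham rate | Expected of 18 / 21 | Chance of none, 18 / 21 | Active rate for 80% power, n = 18 (normal / Fisher) | Same, n = 21 |
|---|---|---|---|---|
| 4.7% | 0.85 / 0.99 | 42% / 36% | 43.3% / 46.6% | 39.6% / 42.0% |
| 6% | 1.08 / 1.26 | 33% / 27% | 45.5% / 49.5% | 41.9% / 44.7% |
| 10% | 1.80 / 2.10 | 15% / 11% | 51.7% / 56.3% | 48.2% / 52.2% |

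Example: sham 6%, active 30%, 21 per group. Here p̄ = 0.18, the null term is √(2 × 0.18 × 0.82/21) = 0.1186 and the alternative term is √[(0.0564 + 0.21)/21] = 0.1126. So (0.24 − 1.96 × 0.1186)/0.1126 ≈ 0.07, and power is about 53%; Fisher gives 42%. With 18 per group the figures are 46% and 34%.

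**5. Could session 10 serve as time zero for relapse?** Only for people already abstinent then. Under the assumed rates that is about one or two of 21 in the sham arm. The subset is also selected after randomisation, so randomisation no longer protects a comparison of the arms within it.

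**The case against.** The best case for the plan is strong in parts. Participants are treatment-seeking, randomised 1:1, masked and handled alike, so the missing quit day does not bias the comparison of abstinence. If active rTMS prompts more people to stop, that is itself a treatment effect. Hypothesis 1 and the named measures of Aim 2 need no quit date, and Aim 2 counts from the last session, which is a workable origin for loss of effect on cigarettes per day or dependence. This is an exploratory R21, and a reduction design is legitimate. Consent pages were removed from the text, so quit advice given only there would not be visible. All of this stands. None of it supplies a starting point for relapse or reconciles the primary-outcome sentence with the observed cigarette.

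A reader might infer more than the documents support.

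- *That the trial cannot answer its objectives.* It can compare cigarettes per day, craving and FTND, and it can compare abstinence without bias, though probably with little information.
- *That end-of-treatment abstinence could reflect only half the course.* This assumes a 7-day window counted back from session 10, which the plan never states. Although "All participants will be treated Monday Friday for 10 treatments", missed days can extend the course, and later sessions could help to sustain abstinence begun earlier.
- *That people who keep smoking tell us nothing about abstinence.* They belong in the denominator as non-abstainers. Only relapse time is undefined for them.
- *That the 41% of smokers reported to have tried to quit can be scaled to this trial.* Section 1 gives no period for that figure, and it describes smokers in general.

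**Conclusion.** The concern holds for one of the two primary efficacy outcomes and for the relapse-time part of Hypothesis 2. As specified, abstinence is likely to yield few events and cannot separate rTMS not helping people to quit from no attempt having been made. Relapse time has no common origin and exists only for those who happen to stop. The craving, cigarettes-per-day and FTND comparisons are not affected.

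The size is illustrative. With assumed sham abstinence of 4.7% to 10%, 1.0 to 2.1 of 21 sham participants would be abstinent, and 80% power with 18 per group would need about 43% to 56% in the active arm. Higher spontaneous quitting would bring more events but would leave the missing time zero as it is.

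Two conditions apply. The contradiction with the observed cigarette depends on that procedure applying at every session, including the tenth, which the text does not settle. The absence of a quit request refers to the visible text; an instruction found only in the consent form would still have to be in the protocol to fix time zero.

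**What to change.** Reconcile Aim 1, Hypotheses 1 and 2, the Craving Assessment item in section 8, the primary-efficacy sentence in section 10 and the Potential Benefits section, and state whether this is a cessation or a reduction trial.

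- **If cessation:** state how and when the quit attempt begins. That is the sponsor's choice and should be identical in both arms. Define relapse and count it from that point. Report abstinence in all randomised participants over the 7 days between session 10 and the 1-week visit, using the diary, CO and cotinine already scheduled there, with the biochemical cut-off stated in advance. Say that the sample size was not set for this outcome.
- **If reduction:** remove abstinence from the primary-efficacy sentence and relapse time from Hypothesis 2, and limit the efficacy conclusion to cigarettes per day and craving.

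Neither route adds a visit or a test. Under the first, abstinence is read one week later, a quit attempt would lower cigarettes per day in both arms, and it must be made consistent with the observed cigarette and the craving ratings that follow it. That is more than a wording change. Under the second, the cessation claim is given up.
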